4. LIST OF ABBREVIATIONS AND DEFINITIONS OF TERMS

The following abbreviations and specialist terms are used in this study protocol.

Table 1: Abbreviations and Specialist Terms

Abbreviation or Specialist Term	Explanation
AAS	Angioedema Activity Score
[REDACTED]	[REDACTED]
AD	atopic dermatitis
AE	adverse event
[REDACTED]	[REDACTED]
ALP	alkaline phosphatase
ALT	alanine aminotransferase
ANCOVA	analysis of covariance
app	application
AST	aspartate aminotransferase
ATC	Anatomic Therapeutic Chemistry
BCRP	breast cancer resistance protein
CFR	Code of Federal Regulations
C _{max}	maximum observed concentration
CONSORT	Consolidated Standards of Reporting Trials
CRO	Contract Research Organization
CSU	chronic spontaneous urticaria
CTCAE	Common Terminology Criteria for Adverse Events
CYP	cytochrome P450
CU	chronic urticaria
CU-Q ₂₀ L	Chronic Urticaria Quality of Life questionnaire
ECG	electrocardiogram
eCRF	electronic case report form
EU	European Union
FAS	Full Analysis Set
Fc ϵ R1	high affinity IgE receptor
FDA	Food and Drug Administration
GCP	Good Clinical Practice
GDPR	General Data Protection Regulation

Abbreviation or Specialist Term	Explanation
GM-CSF	granulocyte macrophage colony-stimulating factor
H1AH	H1 antihistamine
HBV	hepatitis B virus
HCV	hepatitis C virus
HEENT	head, eyes, ears, nose, throat
HIV	human immunodeficiency virus
HRQoL	health-related quality of life
HSS	Hive Severity Score
[REDACTED]	[REDACTED]
ICF	Informed Consent Form
ICH	International Council for Harmonisation
IEC	Independent Ethics Committee
IgE	immunoglobulin E
IgG	immunoglobulin G
IL	interleukin
INR	international normalized ratio
IRB	Institutional Review Board
ISS	Itch Severity Score
[REDACTED]	[REDACTED]
IWRS	Interactive Web Response System
LS	least-squares
MATE	multidrug and toxin extrusion
MedDRA	Medical Dictionary for Regulatory Activities
[REDACTED]	[REDACTED]
MRGPR	mas-related G protein-coupled receptor
NOAEL	no-observed-adverse-effect-level
OATP	organic anion transporting polypeptide
P-gp	P-glycoprotein
PD	pharmacodynamic(s)
PK	pharmacokinetic(s)
PO	oral
PP	Per Protocol

Abbreviation or Specialist Term	Explanation
PQC	product quality complaint
QC	quality control
QD	once daily
RAE	recurrent angioedema
SAE	serious adverse event
SAER	Serious Adverse Event Report
SAP	Statistical Analysis Plan
SOP	standard operating procedure
$t_{1/2}$	half-life
TEAE	treatment-emergent adverse event
Th2	type 2 T helper cells
T_{max}	time to reach maximum observed concentration
TNF- α	tumor necrosis factor-alpha
TPO	thyroid peroxidase
UAS	Urticaria Activity Score
[REDACTED]	[REDACTED]
UCT	Urticaria Control Test
[REDACTED]	[REDACTED]
UGT1A1	uridine 5'-diphospho-glucuronosyltransferase 1A1
ULN	upper limit of normal
US	United States
WHO	World Health Organization

5. INTRODUCTION

5.1. Role of the MRGPRX2 Receptor in the Pathogenesis of Chronic Spontaneous Urticaria

Chronic spontaneous urticaria (CSU; also known as chronic idiopathic urticaria) is a condition characterized by the development of systemic itchy red hives (wheals) and/or deep tissue swelling (angioedema) for periods of at least 6 weeks ([Zuberbier 2022](#)) with no specific eliciting factor. The hives and angioedema associated with CSU are directly attributable to the degranulation of mast cells, which can be triggered by many different stimuli.

The mas-related G protein-coupled receptor (MRGPR) family is comprised of 8 human Class A rhodopsin-like G-protein coupled receptors (MRGPRX1-X4 and D-G) that can sense noxious stimuli and appear to have a role in innate immunity. MRGPRX2 is predominantly expressed in mast cells and has been shown to induce degranulation upon binding to a wide variety of agonists ([Subramanian 2016](#), [Corbiere 2021](#)). MRGPRX2 has been shown to mediate immunoglobulin E (IgE)-independent activation of mast cells, including degranulation and regulation of inflammatory processes. Activation of MRGPRX2 triggers release of proinflammatory mediators and a multicellular signaling cascade that likely plays a key role in multiple human diseases involving clinically relevant mast cell activation, including CSU ([Babina 2020](#), [Thapaliya 2021](#)).

There are several lines of evidence to support a role of MRGPRX2 and IgE-independent mast cell activation in the etiology of CSU. First, many patients with CSU remain inadequately controlled even when receiving antihistamine, with or without concomitant anti-IgE treatment. Second, serum from patients with CSU has been reported to degranulate mast cells lacking the high affinity IgE receptor (FcεR1) to a much larger extent than serum from healthy control subjects ([Bossi 2011](#)), whereas loss of MRGPRX2 reduces degranulation stimulated by CSU patient serum ([Quan 2022](#)). Third, patients with CSU have been reported to have elevated plasma/serum levels of substance P, an agonist of MRGPRX2 ([Metz 2014](#), [Zheng 2016](#)), and a greater number of MRGPRX2 positive mast cells in skin biopsies ([Fujisawa 2014](#)). Finally, and in keeping with the aforementioned findings, patients with CSU have been reported to show enhanced skin reactivity to intradermally injected MRGPRX2 drug ligands ([Shtessel 2021](#)). Overall, these data provide strong support for the potential therapeutic benefit of MRGPRX2 antagonism in the treatment of CSU and warrant further investigation as a novel, IgE-independent, mast cell-specific treatment approach.

5.2. EP262 and Study Rationale

EP262 is a potent small-molecule antagonist of the human MRGPRX2 receptor under development as an orally (PO) administered therapy for CSU.

Preliminary results from Study EP-262-101, a first-in-human randomized, Phase 1 clinical study of single and multiple daily PO doses of EP262 or placebo in 64 healthy subjects, have provided information on the safety, tolerability, and pharmacokinetics (PK) of EP262. Study EP-262-101 also included an initial food effect evaluation. Thirty healthy subjects received a single 50, 150, 400, 800, or 1200 mg dose of EP262. Eighteen subjects received 50, 150, or 300 mg as a multiple dose regimen over 7 days.

All doses evaluated were well tolerated with no dose-limiting adverse events (AEs), early terminations due to AEs, severe AEs, or serious AEs (SAEs) reported. No adverse trends in safety laboratory measures, vital signs, or electrocardiogram (ECG) parameters have been observed. EP262 concentrations increased with increasing single doses in an approximately linear manner and modeling of single dose data predicted multiple dose concentrations. The time to reach the maximum EP262 observed concentration (T_{max}) was achieved on average at approximately 3.2 hours postdose with a half-life ($t_{1/2}$) of approximately 121 hours for the 150 mg dose, driven by an extended terminal elimination phase. EP262 concentrations were approximately 2-fold higher when administered with a high-fat meal than when administered in the fasted state. The absence of safety signals, in conjunction with favorable PK profiles, supports further investigation of EP262 in subjects with CSU in this clinical study.

Study EP-262-201 will evaluate the efficacy, safety, and tolerability of EP262 over 6 weeks of treatment in subjects with CSU. A 6-week treatment duration is deemed adequate based on the anticipated rapid onset of action of EP262 to directly block activation of MRGPRX2 and is consistent with the treatment duration at which efficacy has been demonstrated for other approved and investigational agents.

The primary efficacy measure will be the change from baseline to Week 6 in patient-reported disease activity, as assessed by the Urticaria Activity Score (UAS) over a 7-day period (UAS7), a widely used CSU-specific patient reported outcome measure. Secondary [REDACTED] efficacy measures for this study include the Itch Severity Score (ISS) over a 7-day period (ISS7) and the Hive Severity Score (HSS) over a 7-day period (HSS7), which are the components of the UAS7; [REDACTED]

[REDACTED] Study EP-262-201 will also assess the safety and tolerability of EP262. Collectively, the results will guide further development of EP262, including the design of subsequent confirmatory studies.

The study will be randomized to ensure random allocation of subjects to treatment arms and to reduce bias. Because efficacy assessments have a high degree of subjectivity, the study will be double-blinded. In addition, a placebo-controlled design will be used to control for confounding factors, such as potential Investigator bias, and to ensure that the statistical procedures can be appropriately applied.

5.3. EP262 Dose Rationale

The 150 mg and 50 mg EP262 dose levels to be evaluated in Part 1 of Study EP-262-201 were selected based on a variety of factors to explore efficacy without adversely impacting safety, including results from nonclinical pharmacology studies, nonclinical toxicology studies, and preliminary results from Study EP-262-101, a Phase 1 first-in-human clinical study in healthy subjects.

In vivo results from a transgenic, human MRGPRX2 knock-in mouse model of acute mast cell degranulation demonstrated complete inhibition of vascular permeability by all MRGPRX2 agonists tested at EP262 plasma concentrations of approximately [REDACTED] nM. This was further supported by results from nonclinical studies in a chronic disease mouse model of atopic dermatitis (AD) induced by cutaneous co-exposure to house dust mite extracts and

Staphylococcus aureus Enterotoxin Type B. In the transgenic MRGPRX2 mouse model of AD, treatment produced reductions in disease score, transepidermal water loss, and levels of type 2 T helper cells (Th2) cytokines. Based on several studies in this model evaluating different doses, trough EP262 concentrations of at least [REDACTED] nM were required to yield full attenuation of disease and inflammatory activity. Lower trough concentrations of EP262 did not result in robust disease improvement. Given that MRGPRX2 is activated by numerous agonists and that it is not known which agonist(s) may be the key factors involved in the pathophysiology of chronic urticaria, it is important to select a dose that completely inhibits the multiple agonists tested. Thus, it was assumed that EP262 trough concentrations of [REDACTED] nM or higher will likely be necessary for maximum clinical efficacy.

Consequently, Part 1 of Study EP-262-201 was designed to assess 2 dose levels:

- A dose level of 150 mg, which maximizes the likelihood of observing an impact on pharmacodynamics (PD)/efficacy while falling within exposures that are anticipated to be safe and well tolerated. During the course of the 6-week treatment period, the 150 mg dose is predicted to result in the following:
 - EP262 trough concentrations that exceed the full pharmacologic activity threshold ([REDACTED] nM) while remaining within the range of concentrations achieved in the multiple-dose portion of Study EP-262-101
 - EP262 concentrations that are well tolerated with no undue safety signals based on Study EP-262-101 results at doses [REDACTED] mg
 - EP262 exposure that remains below the exposures associated with the no-observed-adverse-effect-level (NOAEL) in definitive 42-day toxicology studies
- A lower dose level of 50 mg that will target EP262 trough concentrations between [REDACTED] and [REDACTED] nM, which may result in partial pharmacologic activity and will enable dose and exposure response analyses to help better characterize the therapeutic dose range

The PK profile of EP262 in subjects with CSU is anticipated to be similar to that in healthy subjects. To further ensure similar circulating concentrations of EP262 between these two populations, subjects with conditions that may alter PK, such as clinically significant hepatic or renal impairment, are excluded from participating in this study. [REDACTED]

[figure not shown]
5.4. Summary of Benefits and Risks

5.4.1. Benefit Summary

While it is currently uncertain whether patients with CSU will benefit from treatment in this study, nonclinical in vitro and in vivo data, as well as scientific publications implicating MRGPRX2 as a mediator of mast cell degranulation and associated inflammation (Kapp 1991, Morita 1995, Nakamura 2013, Azimi 2017, Nattkemper 2018, Green 2019, Meixiong 2019, Serhan 2019, Ogasawara 2020, Wang 2020, Youngblood 2020, Corbiere 2021), provide compelling support that EP262 has the potential to be an effective treatment for patients with CSU.

[figure not shown]
5.4.2. Risk Summary

The doses evaluated in study EP-262-101 were well tolerated with no dose limiting AEs, early terminations due to AEs, severe AEs, or SAEs reported. Additionally, no adverse trends in safety laboratory measures, vital signs, or ECGs were observed.

5.4.3. Mitigation Strategy

For this initial clinical proof-of-concept study, subjects with clinically significant co-morbidities such as hepatic, renal, or cardiovascular disease will be excluded.

Routine safety measures have been incorporated into the protocol, including AE reviews, vital sign and 12-lead ECG assessments, and laboratory evaluations, including monitoring of bilirubin and management of liver test abnormalities (Section 12.10.3).

5.4.4. Overall Benefit:Risk Conclusion

Overall, the clinical and nonclinical experience to date with EP262 suggests minimal risk to subjects participating in Study EP-262-201. Importantly, there is a clear unmet need for novel treatment options for CSU. Current clinical guidelines recommend second-generation H1 antihistamines (H1AH) as first-line treatment, with the option to increase dosing (Bernstein 2014, Zuberbier 2022), and omalizumab, an anti-IgE monoclonal antibody, or cyclosporine as second-line options for patients who do not adequately respond to antihistamines alone. Nonetheless, nearly 60% of patients continue to experience hives despite treatment with antihistamines, and almost 30% of omalizumab-treated patients report uncontrolled disease, particularly those with moderate-to-severe disease or low serum levels of IgE at baseline (Folci 2018, Maurer 2019, Maurer 2020, Fok 2021). If determined to be effective, EP262 may ultimately have the potential to offer a much-needed novel treatment option for patients suffering from CSU.

6. TRIAL OBJECTIVES AND PURPOSE

Objectives	Endpoints
Primary Objective	
To evaluate the efficacy of EP262 compared to placebo in subjects with chronic spontaneous urticaria (CSU)	
 • Change from baseline to Visit 4 (Week 6) in the sum of the daily UAS over a 7-day period (UAS7)

Secondary Objectives	
To evaluate the safety and tolerability of EP262 compared to placebo in subjects with CSU	
• Type, frequency, and severity of treatment-emergent AEs (TEAEs)• Change from baseline in vital signs, ECGs, and clinical laboratory parameters
To evaluate the efficacy of EP262 compared to placebo in subjects with CSU as assessed by the following: 
• Pruritus severity• Hive severity	
• Change from baseline to Visit 4 (Week 6) in the sum of the daily ISS over a 7-day period (ISS7)• Change from baseline to Visit 4 (Week 6) in the sum of the daily HSS over a 7-day period (HSS7)
Exploratory Objectives	

7. INVESTIGATIONAL PLAN

[figure not shown]
7.1. Overall Study Design

Study EP-262-201 is a Phase 2 randomized, double-blind, placebo-controlled study to evaluate the efficacy, safety, and tolerability of EP262 over 6 weeks in subjects with CSU. The study will be conducted in 2 parts: Part 1 will assess 50 mg and 150 mg doses of EP262 and Part 2 will assess a 25 mg dose of EP262 to further characterize the therapeutic dose range. Part 2 will begin after the last subject is randomized into Part 1. Part 1 and Part 2 are identical in terms of their visit structure, procedures conducted, and the populations being studied. The primary difference between the 2 parts is the EP262 dose levels being assessed. Designated Sponsor (or designee) personnel will have access to unblinded individual subject treatment assignments as described in Section 9.3.2.

Each part includes a Screening Period of at least 2 weeks and up to 30 days to assess subject eligibility that includes collection of the daily UAS score; a 6-week Double-Blind Treatment Period; and a 4-week Safety Follow-Up Period after administration of the last dose of study drug

(EP262 or placebo) for a total study duration of up to approximately 14 weeks for each subject (Figure 1). In Part 1, approximately 114 subjects will be randomized in a 1:1:1 ratio to receive a 150 mg dose of EP262, 50 mg dose of EP262, or placebo PO, once daily (QD) during the 6-week Double-Blind Treatment Period. In Part 2 of the study, approximately 40 subjects will be randomized in a 3:1 ratio to receive either a 25 mg dose of EP262 or placebo PO, QD, during the 6-week Double-Blind Treatment Period. Enrollment of subjects with prior omalizumab use will be limited to 15 subjects in Part 1 and 5 subjects in Part 2.

Figure 1: EP-262-201 Study Design

PO = oral; QD = once daily.

^a Part 2 will begin after the last subject is randomized into Part 1.

^b Any subject who completes the Double-Blind Treatment Period or discontinues study drug (EP262 or placebo) early will have a Safety Follow-Up Visit approximately 4 weeks (± 3 days) after the last dose of study drug.

7.1.1. Screening Period

The Screening Period will consist of 1 study visit (Visit 1). During this period, subjects will undergo assessments to determine study eligibility per inclusion and exclusion criteria and must remain on their prescreening background therapy. Visit 1 (Day -30 to Day -14 [inclusive]) may be conducted over more than 1 day but must be completed between Day -30 and Day -14 (inclusive).

7.1.2. Double-Blind Treatment Period

The Double-Blind Treatment Period will consist of 3 study visits (Visits 2, 3, and 4 [Day 1, Week 3, and Week 6]). During this period, all subjects who meet eligibility requirements will be enrolled into the study and will be randomized on Visit 2 (Day 1) to receive double-blind, QD, PO doses of EP262 or placebo for 6 weeks. In Part 1, subjects will be randomized in a 1:1:1 ratio to receive a 150 mg dose of EP262, 50 mg dose of EP262, or placebo PO, QD. In Part 2, subjects will be randomized in a 3:1 ratio to receive either a 25 mg dose of EP262 or placebo PO, QD. Randomization will be conducted centrally via an Interactive Web Response System (IWRS) and stratified based on prior use of omalizumab (yes/no). QD PO dosing of study drug should occur after at least a 4 hour fast and administered at approximately the same time of day. Subjects should refrain from eating for at least 2 hours postdose. The time and date of all dose

administrations will be recorded in a daily diary. The first dose of study drug will be administered at the clinical site on Visit 2 (Day 1) after all baseline study procedures are completed. Visit 2 (Day 1) will not have a visit window; all other visits in the Double-Blind Treatment Period will have a visit window of ± 3 days. Subjects who discontinue from treatment early should have the Early Treatment Termination Visit conducted as soon as possible after the last dose of study drug, ideally within 2 days after the last dose of study drug. Throughout the treatment period, subjects must remain on their prescreening background therapy, although rescue medication may be taken as needed.

7.1.3. Safety Follow-Up Period

Any subject who completes the Double-Blind Treatment Period or discontinues study drug (EP262 or placebo) early will have a Safety Follow-Up Visit approximately 4 weeks (± 3 days) after the last dose of study drug.

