efficacy assessments will be performed as indicated in the Schedule of Assessments ([Appendix A](#)). Examples of the patient-reported assessments are provided in the appendices but are not to be distributed to subjects for completion. Subjects will be trained on completion of all patient-reported assessments using the study-issued electronic device or application (app).

Urticaria Activity Score Over a 7-Day Period (UAS7)

The UAS is a CSU-specific, 24-hour self-evaluation, patient-reported outcome measure ([Zuberbier 2022](#)). It is based on the assessment of key CSU symptoms: intensity of itch and number of wheals. The UAS scale for both itch and wheal assessment are recorded as a score from 0 to 3 (Total = 0 to

6), with 0 representing no itch/hives to 3 representing intense itch/hives (ie, Itch – interferes with normal daily activity or sleep; Hives – More than 50 wheals). Daily UAS scores are summed over 7 consecutive days to derive the UAS7, with higher scores indicating greater disease severity. Well-controlled urticaria is defined as a UAS7 score ≤ 6 . The [REDACTED]

Subjects will be instructed to complete the UAS daily, in the morning before dosing (as applicable), and at approximately the same time of day, beginning at the Screening Visit to the Safety Follow-Up Visit. The questionnaire will be completed during the Screening Visit. For all other days that coincide with a study visit (for Visit 2 and beyond), the UAS is to be completed in the morning before the study visit.

The UAS scores from Day -7 through Day -1 will be summed to determine subject eligibility for continued participation regarding disease activity. The UAS scores from Day -6 through Day 1 will be summed to serve as the baseline UAS7 score. The 7 daily UAS scores prior to Visit 4 (Week 6) will be summed for primary endpoint analyses. Data from at least 4 of the 7 days for each week are required to be considered an acceptable profile. An example of the UAS7 is included in [Appendix C](#).

[REDACTED]

Safety Assessments

Safety evaluations, including adverse events (AEs), concomitant medications, medical history, vital signs, physical examinations, standard 12-lead ECGs, and laboratory evaluations of safety will be performed as indicated in the Schedule of Assessments ([Appendix A](#)).

Adverse Event Collection

AEs will be documented from the signing of the Informed Consent Form (ICF) until the end of study participation.

Pharmacokinetic Assessments

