7.3. End of Study

A subject is considered to have completed the study if he/she has completed all phases of the study, including the last study visit (ie, the Safety Follow-Up Visit [Visit 5]).

The end of the study is defined as the date of the last study visit of the last subject in the study globally. The end of study may result from the completion of the study according to the protocol or due to early termination by the Sponsor or at the request of a regulatory agency, Institutional Review Board (IRB), or Independent Ethics Committee (IEC) (Section [7.6](#)).

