8.6.1. Discontinuation of Study Drug

Discontinuation of study drug for a subject occurs when the study drug is stopped earlier than the protocol planned treatment duration. Discontinuation of study drug is mandatory in the following instances:

- AEs for which continued exposure to study drug would be detrimental, including AEs that are Common Technical Criteria for Adverse Events (CTCAE) Grade 4 or higher (Section 12.1.2)
- Abnormal liver laboratory results meeting the threshold for discontinuation as listed in Section 12.10.3
- Withdrawal of consent
- Lost to follow-up
- Protocol deviation that results in a significant risk to the subject's safety
- Investigator decision
- Sponsor decision
- Pregnancy during the study (Section 12.2.3)
- Any circumstance that results in a negative benefit:risk balance

For subjects who terminate treatment with study drug early, regardless of the reason, every effort will be made to complete the early treatment termination evaluations as soon as possible after the last dose of study drug, ideally within 2 days after the last dose of study drug.

Whenever possible, subjects should remain in the study and complete the remaining study visits and assessments even when study drug has been discontinued. Subjects who discontinue study drug for any reason and continue with the study visits as planned through Visit 4 (Week 6) (participating only in efficacy and safety, but not PK measures) will participate in the Safety Follow-Up Visit if the last dose of study drug was administered less than 4 weeks before Visit 4 (Week 6) to ensure that at least 4 weeks of follow-up data are collected for all randomized subjects.

If a subject discontinues study drug and chooses not to complete all the remaining study visits, the subject should have the Early Treatment Termination Visit conducted as soon as possible after the last dose of study drug, ideally within 2 days after the last dose of study drug, and a Safety Follow-Up Visit approximately 4 weeks (± 3 days) after the last dose of study drug if at least 4 weeks of follow-up data have not already been collected. If a subject fails to attend the Safety Follow-Up Visit and has not withdrawn consent, all reasonable efforts will be made to contact the subject to ensure that he/she is in satisfactory health. All contacts and contact attempts must be documented in the subject's medical record.

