9.4.1. Screening Period

9.4.1.1. Visit 1 (Day -30 to Day -14 [inclusive])

During the Screening Period, subjects will undergo assessments to determine their study eligibility. Subjects will be screened and should meet all inclusion criteria and none of the exclusion criteria to be enrolled in the study. Any questions regarding eligibility may be discussed with the Medical Monitor.

The following assessments may be conducted over more than 1 day but must be completed between Day -30 and Day -14 (inclusive):

- Completion of informed consent before performance of any study procedures or assessments
- Medical history, including CSU disease history
- Height
- Body weight
- Vital signs
- Physical examination
- Standard 12-lead ECG
- Assessment of baseline concomitant medications, including all medications taken to treat CSU beginning from the date of diagnosis, any prior use of omalizumab, and all medications taken within 14 days before Screening
- AE assessment
- Blood and/or urine sample collection for screening and safety laboratory assessments
- Eligibility check
- Electronic device/app training
- [REDACTED]

Subjects will be instructed to complete the UAS and [REDACTED] daily, in the morning before dosing (as applicable), and at approximately the same time of day, from the Screening Visit to the Safety Follow-Up Visit and the [REDACTED] weekly, in the morning before dosing (as applicable), and at approximately the same time of day, from Day 1 to the Safety Follow-Up Visit using the study-issued electronic device or app. The questionnaires will be completed during the Screening Visit. For all other days that coincide with a study visit (for Visit 2 and beyond), the questionnaires are to be completed in the morning before the visit, unless specified otherwise.

Screening results will be reviewed by the Investigator to determine the subject's eligibility. Subjects who have an exclusionary result during the Screening Period (between Visit 1 and Visit 2) may have that assessment repeated once at the discretion of the Investigator within the screening window and be enrolled if a repeat assessment is within the indicated range as specified in Section 8 for participating in the study. Subjects who are confirmed to be eligible

will be asked to return to the site for Visit 2 (Day 1) to be enrolled and randomized into the study.

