16.2. Estimand

Consistent with the International Council for Harmonisation (ICH) Guideline E9 (R1) addendum on estimands and sensitivity analysis in clinical trials to the guideline on statistical principles for clinical trials ([FDA 2021](#)), the definition of the attributes of the primary estimand of this study is provided in this section.

The primary estimand of the study is to assess the difference in disease activity in pruritus and hives in subjects with CSU treated with EP262 or placebo, as measured by change in weekly UAS7 after 6 weeks of randomized treatment, regardless of treatment discontinuation and use of prohibited and/or rescue medications.

The population targeted by the scientific question is defined via the inclusion and exclusion criteria as part of the protocol. A key aspect of eligibility is that subjects must have moderate-to-severe disease activity in CSU at baseline, defined as a UAS7 of at least 16.

Premature discontinuation from study drug and use of prohibited and/or rescue medications are the primary potential intercurrent events that could occur. The treatment policy strategy is used for the primary estimand, consistent with the intent-to-treat principle.

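### Safety Follow-Up timing is contradictory for subjects who stop drug early, and for some of them it can close the UAS diary before Week 6

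*Protocol*

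**What the plan says.** **Follow-up timing, unconditional.** Protocol 7.1.3 covers completers and early stoppers in one sentence. A subject who "discontinues study drug (EP262 or placebo) early will have a Safety Follow-Up Visit approximately 4 weeks" (±3 days) after the last dose. The same rule stands in note b to the study design figure (Protocol 7.1 and SAP Figure 1), in Appendix A note c and in SAP 3.1.3. None of these carries an exception.

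**Follow-up timing, conditional.** Protocol 8.6.1, repeated in the synopsis and in SAP 4.1.2, asks stoppers to remain in the study where possible. Those who "continue with the study visits as planned through Visit 4 (Week 6") give efficacy and safety data, and have the Safety Follow-Up Visit only if their last dose fell less than 4 weeks before Visit 4. The next paragraph of 8.6.1 deals with the rest: a subject who "chooses not to complete all the remaining study visits, the subject should have the Early Treatment Termination Visit" and then a follow-up visit about 4 weeks after the last dose.

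**End of the diary.** Protocol 9.4.1.1 has the UAS completed daily "from the Screening Visit to the Safety Follow-Up Visit"; the synopsis and SAP 3.4.1.1 agree. No other end point is given.

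**What the analysis needs.** The primary estimand (Protocol 16.2) is the Week 6 change in UAS7 "regardless of treatment discontinuation and use of prohibited and/or rescue medications". SAP 3.4.1.1 requires 4 of 7 daily scores for a weekly value. For early terminators it counts weeks from the first dose, with Week 1 on Days 2-8.

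**The concern.** Two sites could handle the same subject differently. With a last dose on Day 7, a site working from the Schedule of Assessments books the follow-up visit for about Day 35, and the diary stops there. A site working from 8.6.1 keeps a willing subject to Visit 4 with no separate follow-up visit.

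The second problem lies within 8.6.1. A stopper who does not want more clinic visits, but attends the 4-week follow-up, reaches the scheduled end of the diary on that day. Declining clinic visits is not the same as withdrawing consent, yet nothing asks this subject to go on with a two-question diary at home.

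At stake are Week 6 values in early stoppers, whose data after discontinuation a treatment-policy estimand is meant to include. Where those values are missing, the MMRM relies on missing at random (SAP 4.4.3). SAP 4.7 drops the protocol's multiple-imputation sensitivity analysis, so no planned analysis probes that assumption.

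**Working it through.** **Inputs.** Follow-up at last dose + 28 days, ±3 (Protocol 7.1.3). Visit 4 on Day 43 and Visit 5 on Day 71 (Appendix A); 43 + 28 = 71, so the plan itself counts 4 weeks as 28 days. Weekly windows for early terminators start with Week 1 on Days 2-8, and at least 4 daily scores are needed (SAP 3.4.1.1).

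**Week 6 window.** Week k runs from Day 7(k − 1) + 2 to Day 7k + 1. For k = 6 this is Days 37 to 43.

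**Where the two rules differ.** Under 8.6.1 a stayer has no separate follow-up visit if 43 − L ≥ 28, where L is the last-dose day, so for L ≤ 15. For L ≥ 16 the nominal visit falls on Day 44 or later under both rules, after Visit 4. On nominal days the conflict is therefore confined to last doses up to Day 15.

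**Diary days left if the diary closes at follow-up.** The UAS is completed on the morning of a visit, so the visit day counts. Days available in the window = max(0, min(L + offset, 43) − 36).

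| Follow-up offset | Last dose (Day) | Follow-up (Day) | Diary days in 37-43 |
|---|---|---|---|
| +28 | 11 | 39 | 3 |
| +28 | 12 | 40 | 4 |
| +25 | 14 | 39 | 3 |
| +25 | 15 | 40 | 4 |
| +31 | 8 | 39 | 3 |
| +31 | 9 | 40 | 4 |

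The cut-off for a missing Week 6 is a last dose on or before Day 11, or Day 8 to Day 14 across the visit window. The SAP's relaxed rule for short weeks does not rescue it, because fewer than 4 calendar days also gives a missing score.

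**Same last dose under each route (Day 7).**
- Unconditional wording: follow-up on Day 35, no Week 6 diary days.
- 8.6.1, subject stays: 43 − 7 = 36 days, so no separate follow-up visit, and all 7 Week 6 days are scheduled.
- 8.6.1, subject declines clinic visits but attends follow-up: Day 35, no Week 6 diary days.

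**What the model still has in the Day 7 case.** Weeks 2-4 (Days 9-29) are complete, and Week 5 (Days 30-36) has 6 diary days, enough for a valid score. Only Week 6 is lost.

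**Scale.** In an arm of 38, one subject whose model-implied Week 6 value is wrong by d points moves the arm mean by roughly d/38, or about 0.026 points per point of error. The documents give neither d nor the number of such subjects.

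**Power.** The stated figures do not depend on this point, and they reproduce. n = 2(1.645 + 0.842)² × 13²/8² ≈ 32.7, or 33 per group; power at the plan's 34 is 0.81, and at 27 versus 43 it is 0.80.

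**The case against.** The strongest reply is that 8.6.1 is the detailed rule and 7.1.3 a one-sentence overview. Read that way, stoppers are retained, efficacy is collected through Visit 4, and anyone whose last dose was at least 4 weeks earlier has no separate visit to end the diary. This stands. A reader might infer from 7.1.3 that everyone who stops in about the first 11 days leaves before Week 6; 8.6.1, the synopsis and SAP 4.1.2 do not support that.

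A reader might also infer that the follow-up visit always ends participation and triggers device return. Protocol 7.3 defines completion as finishing all phases, "including the last study visit (ie, the Safety Follow-Up Visit [Visit 5"]), so a follow-up visit held while Visit 4 is outstanding does not meet it. Section 11 ties device return to the end of participation, not to a named visit. What closes the diary is the collection period in 9.4.1.1.

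Third, the subjects who leave under the last paragraph of 8.6.1 have chosen not to complete the visits. That is fair, but the choice concerns visits, and the plan never offers the diary alone.

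Fourth, missing Week 6 values are not filled in only from subjects still on drug. The MMRM uses every post-baseline week, starting from an unstructured covariance, and so uses these subjects' own off-drug scores. This limits any bias. Nor do the documents show that early stopping will differ by arm: Protocol 5.2 and 5.4.2 report no early terminations due to adverse events in the Phase 1 study.

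None of this removes the conflict between the passages or the missing diary provision.

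**Conclusion.** The point holds as a wording conflict with a limited data consequence. Five places set the follow-up visit at 4 weeks after the last dose for any early stopper, and 8.6.1 makes it conditional for those who stay. Week 6 UAS7 is lost in two situations only: a site applies the unconditional wording, or a stopper declines the remaining clinic visits and attends the 4-week follow-up. In both, the last dose must fall on or before about Day 11 (Day 8 to Day 14 with the visit window). This rests on the Day 1 anchoring of weeks and on the diary ending at the follow-up visit, as written.

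The number affected cannot be taken from the documents. The 10% early withdrawal rate in Protocol 16.4 covers all early withdrawal, including withdrawn consent, after which no data may be collected; it is not an estimate of diaries closed by this rule. The group is probably small, and no sample-size or power figure changes. It is worth correcting because the missing values are avoidable, fall in the subjects the estimand is meant to include, and meet no planned sensitivity analysis.

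**What to change.** 1. Reconcile Protocol 7.1 (figure note b), 7.1.3, Appendix A note c, and SAP Figure 1 note b and 3.1.3 with Protocol 8.6.1, so that one rule governs follow-up for early stoppers. Which timing suits safety follow-up is for the sponsor to settle; the diary provision below works with either.
2. State in Protocol 8.6.1 and 9.4.1.1 and SAP 3.4.1.1 that, unless consent is withdrawn, daily UAS entry on the device continues through Day 43 (or Visit 4) for every randomized subject, whenever the follow-up visit falls. Device return should come no earlier.
3. In the same edit, say when the diary ends, and how completion under 7.3 is judged, for stayers whose last visit is Visit 4.

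The cost is protocol and SAP wording and a device setting, with no extra clinic visit. A few stoppers keep a two-question diary somewhat longer (8 more days after a follow-up visit on Day 35) and return the device later.
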